Appendix 11 Other Coagulation Indices

For each coagulation time point in [Table 1](#) and Section [6.1.2](#), citrated plasma samples will be collected and frozen for potential analysis of coagulation indices at a later date; these analyses may include, but may not be limited to, the indices listed in the following table:

Antithrombin Activity (ATIII Activity)	Fibrin Monomer
Partial Thromboplastin Time Mixing Studies	Fibrinogen Activity
D-dimer, quantitative	Fibrinogen Antigen
Euglobulin Lysis Time	High-Molecular Weight Kininogen
Factor II Activity	Prekallikrein
Factor IV Activity	Plasminogen Activator Inhibitor-1 Antigen
Factor V Activity	Plasminogen Activator Inhibitor-1 Activity
Factor VII Activity	Plasmin-antiplasmin Complex
Factor VIII Activity	Plasminogen Activity
Factor VIII Antigen Quantitation	Protein C Activity
Factor IX Activity	Protein S Antigen Free
Factor X Activity	Thrombin Time
Factor XI Activity	Tissue Plasminogen Activator Activity
Factor XII Activity	Tissue Plasminogen Activator Antigen
Factor XIII Activity	von Willebrand Factor (vWF) Activity (Ristocetin Cofactor)
	vWF Antigen
	vWF Multimers

ATC	Anatomical Therapeutic Chemical
BMI	body mass index
BP	blood pressure
C	Celsius
CI	confidence interval
cm	centimeter
CRF	case report form
CSR	clinical study report
CTCAE	Common Terminology Criteria for Adverse Events
DOB	date of birth
DOIC	date of informed consent
eCRF	electronic case report form
ECG	electrocardiogram
ECOG	Eastern Cooperative Oncology Group
eGFR	estimated glomerular filtration rate
EOI	end of infusion
EOS	end of study
FLC	free light chain
g/24 hours	grams per day (24 hours)
g	gram
HR	heart rate
ICH	International Council for Harmonisation
IFE	immunofixation electrophoresis
in	inches
IQR	interquartile range
IV	intravenous

Abbreviation	Term
kg	kilogram
L	liter
lb	pounds
m	meter
m ²	meters squared
MedDRA	Medical Dictionary for Regulatory Activities
mg	milligram
mg/dL	milligrams per deciliter
min	minimum
mL	milliliters
mmHg	millimeters of mercury
ng	nanogram
ng/L	nanograms per liter
NT-proBNP	N-terminal pro-brain natriuretic peptide
NYHA	New York Heart Association
PE	physical examination
PEP	protein electrophoresis
PK	pharmacokinetic
PS	performance status
PT	preferred term
PT/INR	prothrombin time/international normalized ratio
PTT	partial thromboplastin time
QT	measure of time between start of Q wave and end of T wave
QTcB	QT formula corrected by Bazett's formula
QTcF	QT interval corrected by Fridericia's formula
RR	respiratory rate or time between 2 consecutive R waves
SAE	serious adverse event
SAP	statistical analysis plan
SD	standard deviation
SF-36v2	Short Form-36 version 2 Health Survey

Abbreviation	Term
sFLC	serum free light chains
SI	Système International unit
SOC	system organ class
TEAE	treatment-emergent adverse event
temp	temperature
ULN	upper limit of normal
vs	versus
WHO	World Health Organization
WOCBP	women of childbearing potential

1. INTRODUCTION

This document outlines the statistical methods to be implemented during the analyses of Study NEOD001-OLE251 (Open-label Extension [OLE] Study to Evaluate the Long-term Safety and Efficacy of NEOD001 in Subjects with Light Chain [AL] Amyloidosis Who were previously enrolled in Study NEOD001-201 (PRONTO)). The purpose of this plan is to provide specific guidelines from which the analyses will proceed. Any deviations from this statistical analysis plan (SAP) will be documented in the clinical study report (CSR).

2. INFORMATION FROM THE STUDY PROTOCOL

2.1. Study Objective

The objective of this study is to evaluate the long-term safety and efficacy of NEOD001 in subjects with AL amyloidosis who completed Study NEOD001-201 (PRONTO).

Safety and efficacy endpoints are detailed in [Section 8](#) and [Section 9](#).

2.2. Study Design

2.2.1. Overall Study Design

This is a global, multicenter, Phase 2b, open-label extension study of subjects with AL amyloidosis who completed Study NEOD001-201. Subjects in this study may receive concomitant chemotherapy.

Subject screening will occur during the 28 days prior to the first administration of study drug (i.e., Month 1-Day 1 Visit), which may overlap with the last visit in Study NEOD001-201. If all eligibility requirements are met, the subject will be enrolled and Screening assessments will be completed. Screening assessments are listed in [Table 1](#).

Study visits will occur every 28 days based on scheduling from Month 1-Day 1. A ± 5 -day window is allowed for visits starting after Month 1. Subjects may receive up to 36 infusions of study drug. Subjects who discontinue study drug before the End of Study (EOS) Visit should have an Early Treatment Discontinuation (ETD) Visit 30 (± 5) days after their final administration of study drug.

2.2.2. Study Drug

Study drug consists of NEOD001. The NEOD001 dose is 24 mg/kg (not to exceed 2500 mg) and will be administered once every 28 (a ± 5 -day window is allowed for visits starting after Month 1) over 60 (± 10) minutes unless a longer infusion duration was established for the individual subject in Study NEOD001-201. The length of the infusion may be extended over a longer period of time when it is clinically indicated. Each vial of 500 mg of NEOD001 will be reconstituted with 9.6 mL sterile water for injection to a concentration of 50 mg/mL, resulting in a buffered, isotonic, preservative-free solution with a total extractable volume of 10 mL. Study drug will be prepared in a 250 mL intravenous (IV) bag of 0.9% saline. The equivalent volume of reconstituted NEOD001 will be withdrawn from the IV bag prior to transferring the study drug solution into the IV bag, such that the total IV bag volume will be 250 mL.

Please refer to the protocol for complete product details.

2.2.3. Study Procedures

The schedule of assessments, as outlined in the study protocol, is presented in [Table 1](#).

Table 1: Schedule of Study Procedures

	Assessment or Procedure	Screening ¹		Treatment ²	Termination
		Days -28 through -1		Monthly Day 1 (±5 days) ³	EOS/ETD ⁴
		<60 days since last visit in Study NEOD001- 201	≥60 days since last visit in Study NEOD001- 201		
	Written Informed Consent	X	X		
	Eligibility Review	X	X		
Clinical	Medical History ⁵	X	X		
	Prior/Concomitant Medications/Therapy ⁶	X	X	X	X
	Adverse Event Assessment ⁷	X	X	X	X
	Physical Exam ⁸	X	X	X	X
	Vital Signs ⁹	X	X	X	X
	ECOG PS/NYHA Class ¹⁰		X	Every 6 months	X
	NIS-LL ¹¹	X	X	Every 6 months	X
	VASPI ¹²	X	X	Every 6 months	X
	SF-36v2 ¹³	X	X	Every 6 months	X
	KCCQ ¹⁴	X	X	Every 6 months	X
	6MWT ^{15,16}	X, X ¹⁷	X, X ¹⁷	Every 6 months ¹⁸	X
	ECG (12-lead triplicate)	X	X	Every 3 months ¹⁹	X
Laboratory ²⁰	Hematology & Chemistry (including amylase and creatine kinase) ²¹	X	X	X	X
	Coagulation – PT/INR, PTT	X	X	X	X
	Coagulation – other indices ²²			Months 1, 12	X
	Troponin T	X	X	X	X
	NT-proBNP ¹⁵	X	X	X	X
	Pregnancy (WOCBP) ²³	X	X	X	X, X ²⁴
	sFLCs		X	Every 6 months	X
	Serum IFE & PEP ²⁵		X	Every 6 months	X
	Urinalysis – Dipstick ²⁶		X	Every 6 months	X
	24-hour Urine Collection:				
	Urine IFE & PEP ²⁴		X	Every 6 months	X
	Urine Protein Excretion		X	Every 6 months	X
	Serum NEOD001 Sample ²⁷			Every 6 months ²⁸	X
Anti-NEOD001 Serum Sample ²⁹	X	X	Every 3 months ²⁸	X	
Study Drug Infusion ³⁰			X		
Vital Status Phone Call				Every 3 months ³¹	

BP = blood pressure; ECG = electrocardiogram; ECOG PS = Eastern Cooperative Oncology Group performance status; EOI = end of infusion; EOS = End of Study; ETD = Early Treatment Discontinuation; HR = heart rate; ICF = informed consent form; IFE = immunofixation electrophoresis; KCCQ = Kansas City Cardiomyopathy Questionnaire; nAb = neutralizing antibody; NIS-LL = Neuropathy Impairment Score – Lower Limbs; NT-proBNP = N-terminal pro-brain natriuretic peptide; NYHA = New York Heart Association; PEP = protein electrophoresis; PK = pharmacokinetic; PT/INR = prothrombin time/international normalized

ratio; PTT = partial thromboplastin time; RR = respiratory rate; 6MWT = 6-Minute Walk Test; SF-36v2 = Short Form-36 Health Survey version 2; VASPI = Visual Analog Scale – Pain Intensity; vWF = von Willebrand Factor; WOCBP = women of childbearing potential. Rescreening is allowed once per subject. Only repeat tests that did not meet eligibility requirements.

1. Individual test results that do not meet eligibility requirements may be repeated; full rescreening is allowed once per subject. Laboratory tests results from Study NEOD001-201 that were performed within 28 days of Month 1-Day 1 may be used for screening in this study.
2. See Protocol sections 6.1.2 and 6.4 for details regarding timing (e.g., pre- vs. postdose) and order of assessments, respectively.
3. Study visits will occur every 28 days based on scheduling from Month 1-Day 1. A ± 5 -day window is allowed for visits starting after Month 1. The predose assessments for each visit may be performed within the 3 days before the visit unless a different timeframe is specified in protocol section 6.1.
4. Conduct the EOS Visit 30 (± 5) days after last administration of study drug. Subjects who discontinue study drug before the end of the study should have an ETD Visit 30 (± 5) days after their final administration of study drug. The assessments shown for EOS/ETD should also be conducted for any unscheduled visit (i.e., a visit not specified by the protocol) as clinically indicated or if deemed necessary.
5. Medical History - Obtain medical history since the subject's last visit in Study NEOD001-201 (including all major hospitalizations and surgeries), as well as the subject's current medical status and therapy for AL amyloidosis.
6. Record all prior/concomitant medications taken or received by a subject within the 28 days prior to the Month 1-Day 1 Visit through the EOS/ETD Visit, and any changes to concomitant medications during the study.
7. Adverse events will be collected from the time that the ICF is signed through 30 days after the last dose of study drug or last study visit, whichever is later.
8. **Screening and EOS/ETD:** conduct a complete physical examination per protocol section 6.5.1.3. **All Other Visits:** conduct a directed physical examination per protocol section 6.5.1.3.
9. Vital signs (HR, BP, RR, and body temperature) - collect after the subject has been at rest for ≥ 5 minutes; within a visit, assess in the same position for all time points. **Month 1:** Within 30 minutes before start of dosing, at EOI (+5 minutes), 30 (± 5) minutes after EOI, and 60 (± 10) minutes after EOI. **All Other Months:** Within 30 minutes before start of dosing, at EOI (+5 minutes), and 60 (± 10) minutes after EOI.
10. See [Appendix 3](#) (ECOG) and [Appendix 4](#) (NYHA).
11. See [Appendix 5](#); NIS-LL is for all subjects who had peripheral neuropathy in Study NEOD001-201.
12. See [Appendix 6](#); VASPI is for subjects who had painful peripheral neuropathy in Study NEOD001-201.
13. See [Appendix 7](#) SF-36v2 should be administered before performing any other study assessments on the same calendar day it is administered.
14. See [Appendix 8](#); administer KCCQ after the SF-36v2, but before conducting any other assessments on the same calendar day it is administered.
15. NT-proBNP should be drawn before conducting 6MWT if being performed on the same calendar day.
16. Collect blood pressure and heart rate pre- and post-6MWT administration.
17. Two pretreatment 6MWTs are required before the first administration of study drug, with a minimum of 4 days between the two tests. The first Screening 6MWT is required to be performed between Days -28 and -5, at least 4 days prior to the second Screening 6MWT, which should be performed within 2 days prior to Month 1-Day 1 (i.e., on Day -2 or Day -1).
18. The postbaseline 6MWTs may be administered on the same calendar day that study drug is administered as long as the NT-proBNP sample is drawn before conducting the 6MWT and the 6MWT is completed before initiation of the study drug infusion.
19. Perform ECGs centrally within 30 minutes before start of dosing and within 15 minutes after EOI.
20. All laboratory tests to be done centrally, unless otherwise noted. Please refer to Laboratory Manual for details. Laboratory tests conducted within 28 days of Month 1-Day 1 may be used for screening.
21. Hematology and chemistry per [Appendix 9](#). Within 3 days before the first day of a new regimen of chemotherapy, conduct an unscheduled central laboratory collection (including hematology, chemistry, PT/INR).
22. Collect citrated plasma samples, which will be frozen for potential analysis of coagulation indices at a later date; see [Appendix 10](#). **Month 1:** EOS/ETD results from Study NEOD001-201 will serve as baseline for this study. Collect sample for vWF activity and antigen assays before dosing on Month 1-Day 1 if they were not tested at EOS/ETD in Study NEOD001-201. **Month 12:** Subjects with defects identified at EOS/ETD in Study NEOD001-201: collect sample and test analytes that were abnormal. All other subjects: collect sample. **EOS/ETD:** Subjects with defects identified at Month 12: collect sample and test analytes that were abnormal. All other subjects: collect sample. **Unscheduled Samples:** collect sample in case of relevant serious adverse events. At any time, if defects are identified, additional analytes will be evaluated, as indicated.
23. Urine pregnancy tests (local) for WOCBP: **Screening:** within 28 days before Month 1-Day 1; **Monthly:** preinfusion; **EOS/ETD:** any time during visit. A positive urine pregnancy test (local laboratory) is to be confirmed with a serum pregnancy test (central laboratory).
24. 90 (± 5) days after last study drug administration (any time during visit) perform urine pregnancy test (local) for WOCBP.
25. The serum and urine PEP must be conducted before the NEOD001 infusion, if being performed on the same calendar day.
26. Urinalysis dipstick per [Appendix 9](#).
27. NEOD001 serum samples (for population PK analysis): **Every 6 months (± 1 month):** within 2 hours before infusion and within 4 hours after EOI; **EOS/ETD:** any time during visit.
28. Collect additional samples as clinically indicated, such as when significant toxicity occurs per protocol section 5.4.2.

29. Anti-NEOD001 serum samples: **Screening:** any time during visit; **Every 3 months:** preinfusion; **EOS/ETD:** any time during visit.

30. Administer over 60 (± 10) minutes unless a longer infusion duration was established for the individual subject in Study NEOD001-201 or during a previous infusion on this study. A minimum of 21 days between doses is required. Subjects should be closely monitored per protocol section 5.3 following completion of the study drug infusion. If chemotherapy is administered on the same day as NEOD001, it must be administered after the NEOD001 observation period.

31. Conduct vital status telephone call approximately 3 months after last study visit and approximately every 3 months thereafter for up to 5 years, death, or subject withdraws consent, whichever occurs first.

2.2.4. Definition of Baseline

2.2.4.1. PRONTO Baseline

The PRONTO Baseline for the 6MWT distance (meters), as defined in the PRONTO SAP, is the longest distance walked prior to the first study drug infusion in the original parent study (NEOD001-201). For all other efficacy and safety parameters, PRONTO Baseline will be defined as the last non-missing assessment prior to the first study drug infusion in the original parent study.

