15. NT-proBNP should be drawn before conducting 6MWT if being performed on the same calendar day.
16. Collect blood pressure and heart rate pre- and post-6MWT administration.
17. Two pretreatment 6MWTs are required before the first administration of study drug, with a minimum of 4 days between the two tests. The first Screening 6MWT is required to be performed between Days -28 and -5, at least 4 days prior to the second Screening 6MWT, which should be performed within 2 days prior to Month 1-Day 1 (i.e., on Day -2 or Day -1).
18. The postbaseline 6MWTs may be administered on the same calendar day that study drug is administered as long as the NT-proBNP sample is drawn before conducting the 6MWT and the 6MWT is completed before initiation of the study drug infusion.
19. Perform ECGs centrally within 30 minutes before start of dosing and within 15 minutes after EOI.
20. All laboratory tests to be done centrally, unless otherwise noted. Please refer to Laboratory Manual for details. Laboratory tests conducted within 28 days of Month 1-Day 1 may be used for screening.
21. Hematology and chemistry per Appendix 10. Within 3 days before the first day of a new regimen of chemotherapy, conduct an unscheduled central laboratory collection (including hematology, chemistry, PT/INR, and PTT).

22. Collect citrated plasma samples, which will be frozen for potential analysis of coagulation indices at a later date; see [Appendix 11](#). **Month 1:** EOS/ETD results from Study NEOD001-201 will serve as baseline for this study. Collect sample for vWF activity and antigen assays before dosing on Month 1-Day 1 if they were not tested at EOS/ETD in Study NEOD001-201. **Month 12:** Subjects with defects identified at EOS/ETD in Study NEOD001-201: collect sample and test analytes that were abnormal. All other subjects: collect sample. **EOS/ETD:** Subjects with defects identified at Month 12: collect sample and test analytes that were abnormal. All other subjects: collect sample. **Unscheduled Samples:** collect sample in case of relevant serious adverse events. At any time, if defects are identified, additional analytes will be evaluated, as indicated.
23. Urine pregnancy tests (local) for WOCBP: **Screening:** within 28 days before Month 1-Day 1; **Monthly:** preinfusion; **EOS/ETD:** any time during visit. A positive urine pregnancy test (local laboratory) is to be confirmed with a serum pregnancy test (central laboratory).

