6.1.2 Treatment Period: Monthly X-Day 1 (± 5 days starting with Month 2)

Study visits will occur every 28 days based on scheduling from Month 1-Day 1. A ± 5 -day window is allowed for visits starting after Month 1. A minimum of 21 days between doses is required. When chemotherapy is administered on same day as NEOD001, it must be administered after the NEOD001 observation period.

Although central laboratory assessments will be performed each month for study analysis, local laboratory assessments may be performed for subject management when necessary for obtaining results on a more immediate basis. Results will be reviewed prior to dosing at each month's Day 1 visit to confirm that continued dosing is appropriate.

An unscheduled central laboratory collection (i.e., hematology, chemistry, PT/INR, and PTT) will be conducted within 3 days before the first day of a new regimen of chemotherapy. An unscheduled sample will be taken in case of a relevant serious adverse event. If defects are identified, additional analytes will be evaluated, as indicated.

Prior to Study Drug Infusion:

The following assessments will be done monthly, unless otherwise specified, prior to dosing on Day 1. The predose assessments may be performed within the 3 days before the visit unless a different timeframe is specified:

- Concomitant medications/therapies
- Assessment of AEs
- Directed physical examination (per Section 6.5.1.3)
- Vital signs (HR, BP, RR, and body temperature; per Section 6.5.1.2) – within 30 minutes before start of dosing, after subject has been at rest ≥ 5 minutes; assess in same position for all time points
- ECOG PS (Appendix 4) – every 6 months
- NYHA class (Appendix 5) – every 6 months
- NIS-LL (Appendix 6) – every 6 months
 - Note: NIS-LL is for all subjects who had peripheral neuropathy in Study NEOD001-201
- VASPI (Appendix 7) – every 6 months
 - Note: VASPI is for subjects who had painful peripheral neuropathy in Study NEOD001-201
- SF-36v2 (Appendix 8) – every 6 months
 - Note: administer SF-36v2 before performing any other study assessments on the same calendar day it is administered
- KCCQ (Appendix 9) – every 6 months
 - Note: Administer after the SF-36v2, but prior to conducting any other assessments on the same calendar day it is administered

- 6MWT (Section [6.5.2.3](#)) – every 6 months – also collect HR and BP pre- and post-6MWT administration

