8.4 Analysis of Efficacy Endpoints

Response rates will be summarized including 95% confidence intervals. The distributions of time-to-event endpoints (progression-free survival, overall survival) will be summarized using the Kaplan-Meier method.

All quantitative endpoints (except 6MWT distance) defined as the change from baseline will be analyzed using linear mixed models for repeated measurements (MMRM). The dependent variable will be the change from baseline at each time point. The model will include fixed effects for time point and treatment-by-time interaction. The baseline value of the corresponding endpoint will be included as a covariate and the unstructured covariance model will be used. The denominator degrees of freedom will be estimated using the Kenward-Roger approximation. The 6MWT distance change from baseline will be analyzed using a Wilcoxon signed rank test.

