2.2.4.2. OLE Baseline

The OLE Baseline for the 6MWT will use the PRONTO Baseline for 6MWT. Otherwise, OLE Baseline is defined as the last assessment prior to first infusion in the OLE.

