4.6. Analysis Visit Windows

Each visit will be denoted by its “month” and “day” such that the first dose day is denoted as Month 1-Day 1; subsequent months will use sequential numbers (e.g., the second dose is administered on Month 2-Day 1). Each infusion is scheduled to be every 28 days (± 5 days) based on the first infusion date. For reporting purposes, the nominal visits will be used for the by-visit analyses. Details of the protocol defined visits and visit windows are given in the protocol and [Table 1](#). In the event of unscheduled visits, re-test assessments, or ETD assessments, these will be reassigned to a scheduled visit for analysis purposes according to [Tables 2, 3, 4 and 5](#).

below. If multiple visits occur within a single visit window, after reassignment of unscheduled visits and ETD visits, then the visit closest to the target day of the visit window will be used in the analysis. If there is a tie, the later visit will be used in the analysis. Unscheduled assessments that do not collect time will not be mapped to any scheduled visit/timepoint.

In data listings, the relative study day from first infusion of all dates will be presented.

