8.8. Functional Endpoint: 6WMT Distance

Subjects will be ranked at each visit ordered from worst to best, based on the completed distance. No imputations for missing data will be made.

Descriptive statistics for 6MWT distance, change from baseline, and percent change from baseline will be presented by visit. The change from baseline at each visit in 6MWT distance will be analyzed using a rank ANCOVA model including the ranked baseline value as a covariate. Estimates of least-square (LS) means, standard errors (StdErr), and 95% CIs will be presented by at each visit.

Only valid assessments 6MWT distance will be included in analysis. Reasons for results being invalid will be presented in a listing and will be finalized prior to database lock. Reasons for results being invalid may include:

- Incorrect course length
- Use of unapproved course
- Unapproved administrator of test
- A site staff member has stopped the stopwatch either inadvertently or incorrectly before the 6 minutes are complete and the subject is still able to walk

Descriptive statistics for observed value, change from baseline, and percent change from baseline will also be presented by visit.

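### The 6MWT baseline is the longest pre-treatment walk but each later visit is a single walk, so the single-group change summaries are shifted toward decline

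*SAP*

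**What the plan says.** SAP Section 2.2.4.1 states that the PRONTO 6MWT baseline "is the longest distance walked prior to the first study drug infusion in the original parent study (NEOD001-201". Section 2.2.4.2 adds: "The OLE Baseline for the 6MWT will use the PRONTO Baseline for 6MWT". No other parameter is treated this way: "For all other efficacy and safety parameters, PRONTO Baseline will be defined as the last non-missing assessment" before the first parent-study infusion, and OLE Baseline is otherwise the last assessment before the first OLE infusion.

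After baseline, Protocol Section 6.1.2 schedules one 6MWT "every 6 months – also collect HR and BP pre- and post-6MWT administration". Where several visits fall in one window, SAP Section 4.6 says "then the visit closest to the target day of the visit window will be used in the analysis", so no maximum is taken after baseline.

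For OLE screening, Protocol Table 1 (footnote 17) says: "Two pretreatment 6MWTs are required before the first administration of study drug, with a minimum of 4 days between the two tests". The second is placed on Day -2 or Day -1. The SAP uses neither of these walks as a 6MWT baseline.

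The two documents analyse the endpoint differently. Protocol Section 8.4: "The 6MWT distance change from baseline will be analyzed using a Wilcoxon signed rank test". SAP Section 8.8 gives descriptive statistics for distance, change and percent change by visit, plus a "rank ANCOVA model including the ranked baseline value as a covariate". SAP Section 10 does not list this replacement. SAP Section 8 treats the OLE Safety Population as one NEOD001 group.

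**The concern.** The longest of several noisy walks overstates a subject's usual distance, and a single later walk does not. Their difference is negative on average when nothing has changed. In a randomized comparison the same offset sits in both arms and cancels. In a one-group summary nothing removes it, and no other provision of the SAP corrects for it. The reader of the OLE tables would see a mean loss of distance, part of which comes from the baseline rule. A true mean gain of the same size as the offset would be reported as no change.

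**Working it through.** **Inputs.** The baseline rule, the single later walk and the single group come from the sections cited above. The documents give no SD, effect size or alpha for the 6MWT and no sample-size basis (Protocol Section 8.6), so there is no figure to reproduce. Assumed: *k* = 2 parent-study walks (the number the OLE protocol requires; *k* = 1 and 3 also checked), within-subject SD *s* of 15 to 30 m, normal walk-to-walk error, and a learning gain *L* of 0 to 2*s*.

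**Step 1: size of the shift without learning.** Let W1, W2 and the later walk Y have the same mean and SD *s*.

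E[Y - max(W1, W2)] = -s/√π = -0.564s

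- s = 15, 20, 25, 30 m gives -8.5, -11.3, -14.1, -16.9 m.
- Each of the three walks is equally likely to be the longest, so an unchanged subject shows a decline with probability 2/3 rather than 1/2.
- *k* = 1 gives 0; *k* = 3 gives -0.85s.

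**Step 2: effect of learning.** Suppose the second walk gains *L* and the gain then holds.

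E[Y - max(W1, W2)] = L[1 - Φ(L/(s√2))] - s√2 φ(L/(s√2))

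| Gain L | Shift | At s = 20 m |
|---|---|---|
| 0 | -0.56s | -11.3 m |
| 0.5s | -0.35s | -7.0 m |
| 1s | -0.20s | -4.0 m |
| 2s | -0.05s | -1.0 m |

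Under the same conditions the last walk as baseline has expected change L - L = 0 whatever *L* is. The mean of the two walks gives L - L/2 = +L/2, a shift toward improvement.

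**Step 3: the SAP's rank ANCOVA.** With one group, the LS mean at the mean baseline rank equals the mean of the response ranks, (n + 1)/2. For n = 60 it is 30.5, and simulated data gave 30.5 whether the true shift was 0, -50 or -200 m. It does not test change against zero, so the baseline offset cannot move it.

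**Step 4: the protocol's Wilcoxon test, if applied to this baseline.** Rejection rate of a two-sided 5% test (level assumed) with zero true mean change, *k* = 2, no learning, 4,000 simulated studies per cell. Here τ is the SD of true individual change.

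| n | τ = 0 | τ = 1s | τ = 2s | τ = 3s | τ = 5s |
|---|---|---|---|---|---|
| 20 | 44.5% | 28.5% | 16.0% | 10.5% | 6.9% |
| 50 | 84.1% | 63.4% | 36.6% | 21.1% | 11.9% |
| 100 | 98.6% | 91.9% | 62.0% | 38.1% | 18.1% |

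Almost all rejections are in the direction of decline. With the last walk as baseline the rate is 4.2% to 5.6% across n = 20 to 100 and the same τ. With learning (n = 100, τ = 1s, 3,000 runs), the longest-walk rate falls to 53.5%, 21.0% and 5.1% for gains of 0.5s, 1s and 2s.

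**The case against.** A reader might infer that the planned 6MWT analysis has a badly inflated false-positive rate and invalid confidence intervals. For example, with assumed *s* of 15 to 30 m, 60 to 80 subjects and an SD of change of 50 to 70 m, a normal test of zero change rejects roughly 16% to 86% of the time. The documents do not support that as a property of the SAP analysis. The longest-walk baseline is in the SAP; the signed rank test is only in the protocol, which gives no rule for combining its screening walks. The SAP replaces that test with a rank ANCOVA whose LS mean is fixed (Step 3). The range also rests on assumed SDs, n and walk count, and it ignores learning. With s = 20 m, n = 80 and an SD of change of 70 m, a 20 m learning gain cuts the rejection rate from 30% to about 8% (4.0/(70/√80) = 0.51 standard errors). Zero change is in any case not a null of no drug effect here, because disease course and concomitant chemotherapy also enter.

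Three further points can be made for the plan. The rule is carried over from the PRONTO SAP for continuity, and it cancels in a comparison of parent-study arms. That is fair, but the SAP states no such 6MWT test, and the OLE Safety Population summary has one group. Next, the parent-study walk count is unseen; the word longest implies more than one walk, but the documents do not show it. Last, the direction is conservative for efficacy. That stands, but a study whose objective includes long-term efficacy should not report a decline that its baseline rule produces.

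**Conclusion.** The concern holds for the change and percent change in distance reported within one group. The shift is toward decline, up to about 0.56 within-subject SD with two equally noisy walks (-8 to -17 m for *s* of 15 to 30 m). It is about 0.20 SD with a 1 SD learning gain, near zero at 2 SD, and zero for a subject with one walk. The direction and mechanism follow from the documents if more than one walk was done; the size depends on assumptions they do not settle. Rejection above the nominal level would arise only if the protocol's Wilcoxon test were run on this baseline.

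The OLE Baseline has a related weakness. It predates the whole parent study, so OLE change for this endpoint also includes whatever happened during that study. This is one descriptive endpoint in a study with no primary hypothesis, so the point is worth correcting but does not threaten the study's other results.

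**What to change.** For the within-group 6MWT change and percent-change summaries, amend SAP Sections 2.2.4.1 and 2.2.4.2:

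- **PRONTO Baseline:** the last valid walk before the first parent-study infusion.
- **OLE Baseline:** the last valid walk before the first OLE infusion, which the protocol already places on Day -2 or Day -1.
- **Sensitivity analysis:** repeat the summaries with the longest-walk baseline, for continuity with the parent study.

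This is the rule the SAP already applies to every other parameter. The last walk is preferable to the mean of the walks because it stays unbiased when a learning gain has occurred and then holds (Step 2).

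The cost is SAP wording and one extra set of summaries; no new data are needed. The main 6MWT baseline would differ from the parent-study definition. Individual changes would be slightly noisier: for a stable subject, SD √2·s = 1.41s against √(2 - 1/π)·s = 1.30s. If learning continued after baseline, the last walk would lean toward improvement, which is a further reason to show both versions. SAP Section 10 should also record the replacement of the Wilcoxon test by the rank ANCOVA, so that the two documents agree on what is tested.
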